8.2.2.1 SLEEP APNEA HISTORY – TREATED, MILD, NONE

Participants who have documented treated, mild, or no OSA may not be required to complete HSAT testing. Documentation must be valid, such as a participant's medical record or information from a positive airway pressure (PAP) device app; ascertainment of OSA status cannot be based only on participant self-report. With documentation of adequately treated, mild, or no OSA, participants may proceed to the evaluation of their sleep phenotype based on their PROMIS 8a SRI and 8b SD scores (see Figure 3). In some instances, the investigator may need to adjudicate OSA status. Appendix-level eligibility criteria will be applied to determine if participants will progress to Baseline assessments (Section 8.3) or be re-evaluated for another phenotype. Participants eligible for Baseline assessments will first sign an informed consent form for their respective phenotype appendix.

If documentation of sleep apnea testing and/or treatment was more than 6 months prior or documentation does not exist, participants may be required to complete HSAT testing pending investigator discretion (see Section 8.2.2.2).

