Participants will be initially pre-screened for trial entry over the phone. If they pass this screening, participants will undergo informed consent for the platform protocol, followed by assessment with both the PROMIS 8a SRI and 8b SD. Participants with adjusted T scores less than 60 on both assessments will be considered screen failures, but those scoring 60 or greater on either will proceed to SRBD screening (green box). Participants who have documentation within the past 6 months verifying they have adequately treated, mild, or no sleep apnea will proceed to the phenotype assessment (red box). Participants will be marked as untreated or unknown if they do not have documentation within the past 6 months verifying they have adequately treated, mild, or no sleep apnea; unknown can also refer to being treated with non-PAP treatments. These participants will be referred for HSAT (yellow hatched box). After completing HSAT, participants will need to follow-up for another inperson visit or phone call to review sleep apnea test results and determine continued trial eligibility. Participants identified with untreated moderate or severe Obstructive Sleep Apnea (OSA) or inadequately treated OSA will be referred to clinical care for initiation or modification of OSA treatment. Assuming testing and treatment for sleep apnea are adequate after clinical intervention, participants will retake the PROMIS 8a SRI and 8b SD and, if still eligible, proceed to phenotype assessment (red box); however, if their sleep symptoms improve after diagnosis and treatment of OSA (both T scores <60), they will be ineligible for study participation. The participants' phenotype – hypersonnia or complex PASC-related sleep disturbance – will be determined by their PROMIS 8a SRI and 8b SD scores coupled with several simple, self-reported sleepsymptom questions. Based upon their phenotypes, participants will be assigned to a specific trial appendix. Appendix-level exclusion criteria will be applied to classify participants as screen failures or eligible for Baseline assessments. Eligible participants will consent to the appendix before starting Baseline activities. At the Baseline visit, participants will complete the appendix-level activities and be randomly assigned to an intervention group. Participants will proceed to pre-intervention and intervention activities. Then, they will return for an EOI clinic visit comprising the listed activities. Finally, participants will be contacted by phone on or around 30 days after the End of Study Clinic Visit for a final safety assessment. For greater workflow detail, see Section 8.

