8.2.2 SCREENING

Information about the study will be presented to potential participants and questions will be asked to determine potential eligibility. *Study-specific screening procedures will begin only after informed consent for the platform protocol is obtained*. Informed consent may be obtained via paper or online forms.

The PROMIS 8a SRI and 8b SD will be the first procedure completed after obtaining consent. The PROMIS 8a SRI and 8b SD may be administered over the phone, by mail, in-person, or electronically. Both the 8a SRI and 8b SD will be administered, but which one serves the primary endpoint is defined in each appendix. Moreover, both will be completed as the first study procedure so that participants who score below 60 on both the 8a SRI and 8b SD (screen failure) will not be required to complete the remaining screening procedures. Conversely, participants who score 60 or greater on either the 8a SRI or 8b SD (eligible) will complete the Sleep-screening questions, which are several self-reported sleep-symptom questions. Based on their answers, they will screen fail or proceed to a sleep apnea history examination and the other screening procedures, which include the following:

- Demographics
- Concomitant medications, review of the previous 14 days
- Medical history, including SARS-CoV-2 infection history and PASC symptoms and duration

- Pregnancy test, urine or serum, for individuals of childbearing potential
- Nasal swab for SARS-CoV-2, using rapid antigen test or PCR test
- Screening blood labs, dependent on PROMIS 8a SRI and 8b SD scores

Screening procedures may be performed over 1 or 2 calendar days. Baseline assessments, specimen collection, and the initial study intervention administration can occur on the same calendar day. For some participants, SRBD¹ screening will reveal the need for further testing and treatment. This process (including HSAT device delivery, data collection, device return, data analysis, and treatment) may take 6 weeks or more.

All participants will undergo SRBD screening.

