8.2.2.2 SLEEP APNEA HISTORY – UNTREATED, UNKNOWN

Participants who have untreated or unknown sleep apnea or have not completed sleep apnea testing within 6 months of informed consent will be required to complete HSAT testing. Similarly, participants who have their OSA treated prior to screening with a therapy other than a PAP therapy, such as an oral appliance, hypoglossal stimulation, bariatric surgery, or other conservative treatment, will be referred to HSAT testing using the device or therapy that had been previously prescribed. Participants will receive a HSAT device with use instructions, access to an instructional video, and discussion of HSAT results. Participants will be required to return their HSAT device.

If the participants' HSAT data reveal they have no or mild OSA (an apnea hypopnea index <15) and no evidence of other significant SRBD (central apnea index <10; duration of Cheyne-Stokes breathing <10 minutes; percentage estimated sleep time at an oxyhemoglobin saturation <88% [T88] <10%;), they will retake the PROMIS 8a SRI and 8b SD and, providing an eligible score, proceed to the other screening procedures listed below.

If the participants' HSAT data reveal they have CSA, Cheyne-Stokes breathing, or hypoxemia, then participants will be considered a screen failure and referred to routine clinical care.

¹ includes evaluation of OSA and CSA, Cheyne-Stokes breathing, and hypoxemia unexplained by OSA

If they are found to have OSA that is moderate or severe (an apnea hypopnea index/respiratory event index >15), then PAP treatment is required for further study participation. Participants will be referred to local health care providers for review of the HSAT results and other relevant clinical information. If PAP treatment is determined to be appropriate and prescribed, participants may receive a study-issued, auto-titrating PAP device. Participants will be counseled on treatment and adherence (Section 8.2.2.3). Adequate adherence is necessary for continued study participation. PAP devices that are study-issued do not have to be returned.

This evaluation and treatment process may take 6 weeks or more. Participants who do not seek, initiate, or adhere to treatment will be ineligible to proceed. If 7 or more days elapse since the PROMIS 8a SRI and 8b SD were last assessed, participants will retake the PROMIS 8a SRI and 8b SD. If they provide an eligible score, they may proceed to the other screening procedures, which include the following:

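### Section 8.2.2.1 makes home sleep apnea testing discretionary when documentation is outdated or absent, contradicting Section 8.2.2.2 and the schema; with no record at all, exclusion 3 could go unverified

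*Protocol*

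**What the plan says.** Section 8.2.2.1 covers participants with treated, mild or no sleep apnea. It asks for valid documentation, for example a medical record or "information from a positive airway pressure (PAP) device app", and adds that "ascertainment of OSA status cannot be based only on participant self-report". It also allows the investigator to adjudicate OSA status in some instances. It then sets this condition: "If documentation of sleep apnea testing and/or treatment was more than 6 months prior or documentation does not exist". In that case, "participants may be required to complete HSAT testing pending investigator discretion", with a pointer to Section 8.2.2.2.

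Section 8.2.2.2 covers untreated or unknown status. Participants in either state, and those who "have not completed sleep apnea testing within 6 months of informed consent will be required to complete HSAT testing", have no discretionary route.

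The schema text in Section 1.2 takes the same line: "Participants will be marked as untreated or unknown if they do not have documentation within the past 6 months" showing adequately treated, mild or absent apnea. Those so marked are then referred for HSAT. The text under Figure 2 makes participants who choose not to be tested ineligible.

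Footnote 5 to Table 2 (Appendix A) and footnote 19 to Table 3 (Appendix B) share one sentence, which waives SRBD screening/HSAT for a participant with a sleep apnea screening and documented adherence in the 6 months before Screening. Section 8.2.2 states: "All participants will undergo SRBD screening".

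**The concern.** The same participant falls under a discretionary rule in one section and a mandatory rule in the next. With approximately 25 to 100 sites planned (synopsis), a site working from Section 8.2.2.1 and a site working from Section 8.2.2.2 could reach different eligibility decisions for the same kind of person.

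The decision matters because exclusion 3 in Section 5.2 is set by measured quantities: an apnea hypopnea or respiratory event index of at least 15, a central apnea index, a duration of Cheyne-Stokes breathing, and time at low oxygen saturation. Unlike several neighboring criteria, it is not limited to *known* disease, so the absence of a diagnosis on file does not satisfy it.

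Section 4.2 explains why the exclusion is there. Untreated severe apnea can blunt the effect of treatments for other sleep disorders. Wake-promoting drugs, which Appendix A tests, should not be given to patients with untreated OSA unless treatment of the OSA has failed or was not tolerated. Section 4.2 also lists daytime sleepiness among the consequences of OSA, so undetected OSA can look like the hypersomnia phenotype. The stakes are therefore possible dilution of the treatment effect and a safety and eligibility inconsistency.

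**Working it through.** No arithmetic applies, because the protocol gives no figure for this point. The check sets the rules side by side for two kinds of participant.

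| Place | No record at all | Record older than 6 months |
|---|---|---|
| 8.2.2.1 | HSAT discretionary | HSAT discretionary |
| 8.2.2.2 | HSAT mandatory | HSAT mandatory if the last test was more than 6 months before consent |
| 1.2 schema | Marked unknown, referred for HSAT | Marked unknown, referred for HSAT |
| Footnotes 5 and 19 | Waiver does not apply | Waiver does not apply |

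**Step 1: is there a conflict?** Yes. Section 8.2.2.1 says *may* for exactly the participants for whom Section 8.2.2.2 says *will*. The pointer from the first to the second joins the two sentences without ranking them.

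**Step 2: how many places contradict Section 8.2.2.1?** Two do so expressly: Section 8.2.2.2 and the schema. The footnotes state one circumstance in which testing is unnecessary. They agree with the stricter rule only by implication, and they are one sentence used twice.

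**Step 3: what follows if the discretion is used to waive HSAT?**
- *No record.* There is no medical record, no PAP download and no HSAT result. Self-report cannot stand alone. Adjudication is permitted, but there is no objective measurement to adjudicate. Exclusion 3 cannot be verified.
- *Older record.* A dated objective source exists. Exclusion 3 can be assessed from it, though not from current data. The problem is only that the sections disagree.

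**Step 4: does any group need protecting from a simple switch to *will*?** Yes. A PAP user with an old diagnostic test but current device data may proceed under Section 8.2.2.1 and the schema. Read literally, the Section 8.2.2.2 trigger, which looks only at the date of testing, would catch that person too.

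**Step 5: can the harm be sized?** No. That would need the share of participants without records, the rate at which investigators would forgo HSAT, and the prevalence of an index of at least 15 in this population. The protocol gives none of these. The 9% to 38% for OSA in Section 4.2 refers to adults in general and is not tied to that threshold.

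**The case against.** The best defense is that the protocol, read as a whole, already routes the participant with no record. The schema marks that person as unknown, Section 8.2.2.2 is headed for untreated and unknown status, and the disputed sentence sends the reader there. Exclusion 3, universal SRBD screening and the bar on self-report all still bind, so an investigator who waived HSAT with no record would breach other provisions. On this view the word *may* is loose drafting.

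Much of this stands. It shows what the sponsor most likely intended, and it means that enrolling an unmeasured participant requires reading Section 8.2.2.1 in isolation. It does not remove the conflict. Section 8.2.2.1 expressly names the case where no documentation exists and expressly grants discretion in it, and nothing says that Section 8.2.2.2 prevails.

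A reader might infer that exclusion 3 loses its source in every case the sentence covers. It does not, because an older record is still a source. A reader might also count the footnotes as two further contradictions. Their wording gives a sufficient condition for waiver and does not itself order testing in all other cases.

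**Conclusion.** The contradiction is certain on the text. For outdated documentation it is an inconsistency between an express discretion and two express directions to test. For absent documentation it goes further: using the discretion leaves no objective basis for an exclusion that is defined by measurements. The second conclusion assumes that *no documentation* means no objective record of any kind, and that a site acts on Section 8.2.2.1 as written. The Manual of Procedures may guide sites, but it is not available here and the protocol text conflicts on its face.

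The size of the effect is not estimable. A reader might infer bias between treatment groups, but Section 8.3 places randomization after screening and Baseline assessments, so any undetected OSA would enter before allocation. The possible harm is dilution and inconsistent eligibility. The point should be corrected; it does not invalidate the design.

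**What to change.** In Section 8.2.2.1, reword the sentence so that HSAT is mandatory when no valid objective documentation of OSA status exists.

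For documentation older than 6 months, choose one rule. The default should be the stricter one that Section 8.2.2.2 and the schema already state. If the sponsor prefers discretion for an older objective study, that is its choice to make and state openly, but the protocol does not presently support it outside Section 8.2.2.1.

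Say explicitly that PAP users with valid adherence data from the past 6 months may proceed even if the diagnostic test is older, as Section 8.2.2.1 and the schema allow. Use the same wording in Sections 8.2.2.1 and 8.2.2.2, the schema text, and footnotes 5 and 19.

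The cost is a few sentences of protocol text, an unknown number of additional HSATs, and longer screening for those participants. On timing, Section 8.2.2 warns: "This process (including HSAT device delivery, data collection, device return, data analysis, and treatment) may take 6 weeks or more". No new procedure is introduced, because HSAT is already part of the plan.

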8.2.2.2 SLEEP APNEA HISTORY – UNTREATED, UNKNOWN

Participants who have untreated or unknown sleep apnea or have not completed sleep apnea testing within 6 months of informed consent will be required to complete HSAT testing. Similarly, participants who have their OSA treated prior to screening with a therapy other than a PAP therapy, such as an oral appliance, hypoglossal stimulation, bariatric surgery, or other conservative treatment, will be referred to HSAT testing using the device or therapy that had been previously prescribed. Participants will receive a HSAT device with use instructions, access to an instructional video, and discussion of HSAT results. Participants will be required to return their HSAT device.

If the participants' HSAT data reveal they have no or mild OSA (an apnea hypopnea index <15) and no evidence of other significant SRBD (central apnea index <10; duration of Cheyne-Stokes breathing <10 minutes; percentage estimated sleep time at an oxyhemoglobin saturation <88% [T88] <10%;), they will retake the PROMIS 8a SRI and 8b SD and, providing an eligible score, proceed to the other screening procedures listed below.

If the participants' HSAT data reveal they have CSA, Cheyne-Stokes breathing, or hypoxemia, then participants will be considered a screen failure and referred to routine clinical care.

¹ includes evaluation of OSA and CSA, Cheyne-Stokes breathing, and hypoxemia unexplained by OSA

If they are found to have OSA that is moderate or severe (an apnea hypopnea index/respiratory event index >15), then PAP treatment is required for further study participation. Participants will be referred to local health care providers for review of the HSAT results and other relevant clinical information. If PAP treatment is determined to be appropriate and prescribed, participants may receive a study-issued, auto-titrating PAP device. Participants will be counseled on treatment and adherence (Section 8.2.2.3). Adequate adherence is necessary for continued study participation. PAP devices that are study-issued do not have to be returned.

This evaluation and treatment process may take 6 weeks or more. Participants who do not seek, initiate, or adhere to treatment will be ineligible to proceed. If 7 or more days elapse since the PROMIS 8a SRI and 8b SD were last assessed, participants will retake the PROMIS 8a SRI and 8b SD. If they provide an eligible score, they may proceed to the other screening procedures, which include the following:

- Concomitant medications, review of the previous 14 days
 - Only if the Screening review occurred more than 14 days prior
- Pregnancy test, urine or serum, for individuals of childbearing potential
 Only if the Screening test occurred more than 3 days prior
- Nasal swab, for SARS-CoV-2 using rapid antigen test or PCR test
 - Only if the Screening test occurred more than 3 days prior
- Screening blood labs, dependent on PROMIS 8a SRI and 8b SD scores

Appendix-level eligibility criteria will be applied to determine if participants will progress to Baseline assessments (Section 8.3) or be re-evaluated for another phenotype. Participants eligible for Baseline assessments will first sign an informed consent form for their respective phenotype appendix.

8.2.2.3 TREATMENT ADHERENCE

See the MOP for definitions on adequate adherence.

8.3 BASELINE (DAY 0)

Baseline assessments may occur on the same day as Screening, depending on each patient's time availability and tolerance. If not on the same day, Baseline assessments may be divided into home and in-person assessments in order to reduce in-person burden time. For example, the PROMIS 8a SRI and 8b SD, secondary outcome measures, and exploratory PROs could be administered at home before the in-person visit, which would be used for completing the remaining assessments and procedures. Regardless of their order or location, the following assessments and procedures comprise the Baseline visit:

- Concomitant medications, collected for medications taken in the past 14 days, and alternative therapies
 - Only if the Screening review occurred more than 14 days prior
- Pregnancy test, urine or serum, for individuals of childbearing potential
 - o Only if the Screening test occurred more than 3 days prior
- Nasal swab, for SARS-CoV-2 using rapid antigentest or PCR test
 - Only if the Screening test occurred more than 3 days prior
- PROMIS 8a SRI and 8b SD
 - o Only if the Screening test occurred more than 7 days prior

- o If multiple assessments are performed, the most recent score is used for inclusion.
- Height and weight
 - Height may be obtained by self-report for participants who are unable to stand or by medical record.
 - Weight must be obtained from a scale.
- Sleep Phenotype questionnaire
- PROMIS 10a Fatigue
- Neurocognitive Battery
- ECog2
- PASC Symptom Questionnaire
- Insomnia Severity Index (ISI)
- Orthostatic Hypotension Questionnaire (OHQ)
- Modified DePaul Symptom Questionnaire-Post-Exertional Malaise (DSQ-PEM)
- Patient Global Impression of Severity (PGIS)
- SASS-Y, only for the Complex PASC-Related Sleep Disturbance appendix
- Sleep diary, distributed for participants to complete during pre-intervention
- Activity tracker, distributed for participants to wear during pre-intervention
- Blood collection, for clinical labs; timing and type may differ for each appendix
- Biorepository, for blood and stool; see Section 8.9
- Safety assessment, including serious adverse events (SAEs) and suspected unexpected serious adverse reactions (SUSARs)

See each appendix for additional procedures. Refer to the MOP for details of these procedures.

After completing Baseline assessments, participants will be randomized to an intervention group within their assigned appendix, which is based on their sleep phenotype.

After randomization, pre-intervention activities must begin within 48 hours of completing Baseline assessments, as applicable per appendix.

8.4 PRE-INTERVENTION AND INTERVENTION

8.4.1 PRE-INTERVENTION

Participants will complete the sleep diary and wear the activity tracker for 7 days. The activity tracker should be worn at all times during the 7 days except when charging. Other activities may occur according to each appendix.

8.4.2 INTERVENTION

The Intervention type and duration are specific to each appendix. See appendices for necessary inperson visits.

Wearing the activity tracker during the entire intervention is optional, but doing so should be encouraged. Not wearing the activity tracker during the entire intervention will not prompt a deviation.

Additionally, the following will occur by phone call. Refer to appendices for intervention-specific timing of this phone call.

- Safety assessment including SAEs, SUSARs, and events of special interest (ESIs)
- Intervention adherence evaluation, see appendices
- Healthcare Encounter survey

At each patient contact during the intervention, safety assessments will be assessed and the Healthcare encounter survey will be administered.

The final week of the intervention period will include the EOI Clinic Visit.

